While for some surgeries, a waiting time to surgery of months is not an unusual eventuality (e.g., some elective orthopaedic surgeries), this is a more unique circumstance for other major elective noncardiac surgeries. Therefore, to identify surgical candidates time before their surgery, and follow them up for a certain time before their surgery is often impracticable. Due to the COVID-19 contingency, we now have a sample of patients that, due to the deferral of their surgery we are capable of following and assessing for their cognitive status before they receive their surgery, for one to a few months. In this way, we will be able to draw preoperative individual-specific trajectories of cognitive performance, which represent an intra-individual comparison to the postoperative cognitive performance, to evaluate the relative and absolute impact of surgery on our older patients.

We expect that the COVID-19 pandemic, and the imposed social distancing, is having an impact on older patient lives, and also on older patients that are waiting for their surgery. Changes in their ability to live a normal life because of the current restrictions might translate into changes in their physical performance, and might have an impact on their mood and also on their perception of pain, and eventually translate into changes in their cognitive performance. The deferral of their surgery *per se*, and the possible adoption of adjuvant

therapies in the meantime, might have, at least theoretically, an influence on their overall performance. For all these reasons, we might see a different preoperative cognitive trajectory, compared with what we would have seen in a non-COVID-19 time. However, if surgery has an impact on our patient cognition, we still expect to see it as a postoperative change (e.g. a greater decline, a change in slope) compare to their actual preoperative trajectory, so that the performance we see at 3, 6 or 12 months after surgery is worse than what we would expect based on the preoperative trajectory.

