3.5 Sample size

The slowdown of the operating rooms due to COVID-19 started in mid-March, and it will last at least until the end of June or July at the participating sites. We expect to recruit 330 participants between May and August 2020. This sample size will be sufficient to test our primary hypothesis that, on average, in our population, the cognitive performance at 6 months after surgery will be worse, in a clinically significant way, compared to what we would expect based on the preoperative trajectory. We will base our primary hypothesis on the performance at the *One-Back Task (OBK)* of the CBB, at 6 months after surgery. The *OBK* assesses working memory, which is a cognitive domain often found altered in the context of postoperative cognitive dysfunction. It uses a well-validated n-back paradigm with stimuli from playing cards. The subject is asked whether the card displayed in the center of the screen is the same as the card presented immediately before. The subject responds by pressing the “yes” or “no” key. The primary outcome variable for this test is accuracy of correct response, normalized using an arcsine square-root transformation. In **APPENDIX II** we provide a table summarizing the clinical relevance of the test and its results, with data on the difference in performance between healthy older adults, and older adults with mild cognitive impairment (MCI) or dementia based on standardized neuropsychological assessment.^{13 19} Based on the literature, a typical score of healthy older adults is 1.35; the average difference, at one time point, in the *OBK* score, between healthy older adults and older adults with mild cognitive impairment (MCI), and older adults with dementia, is, respectively, 0.07 and 0.17.^{13 19} We hypothesize that in our study population we will see a preoperative trajectory, which, if it continued, unchanged, after surgery (H_0), would lead to an average decrease in OBK score of 0.009 over 6 months. This is still consistent with a decline over time compared with what we would expect on average in a healthy older population.^{13 19} Our hypothesis (H_1) is that surgery will change the preoperative trajectory so that at 6 months after surgery we will instead see an average decrease, compared with right before surgery, of 0.035 (which would correspond to the average change in a hypothetical population in which 40% of subjects experience a decline of at least 0.07, 50% no

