change, and 10% an improvement of 0.07). Based on a test of comparison of means in one sample, with an alpha error of 0.05 (2-tailed), and a standard deviation for the OBK score of 0.16,¹³ to enrol 330 subjects will be sufficient to test our hypothesis with 80% of power, even in case of an attrition rate as high as 10%.

Recruiting 330 participants is a feasible goal based on the current status of knowledge about the COVID-19 contingency plan. The lockdown of the operating rooms started in March and will last at least until the end of June, or longer, depending on the participating site. During the lockdown, we expect to be able to enroll at least 120 participants at McMaster sites, and 30-50 participants at each of the other participating sites. Even when the operating rooms will reopen to more elective surgeries in the next months, this will happen slowly, so that we expect a carryover of the lockdown at least until the end of the summer. Moreover, it is projected that, if countries increase their normal surgical volume by 20% post-pandemic, it would take a median 45 weeks to clear the backlog of operations resulting from COVID-19 disruption.²⁰ Therefore should we see a recruitment rate slower than expected, for any reason, we will extend our recruitment period to beyond the summer.

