3.6.1 Primary analysis

We will report descriptive summary statistics of the performance of the study population at each of the 4 CBB tasks for each of the preoperative and postoperative time points. We will also represent individual and averaged performance trajectories graphically.

To explore whether surgery has a statistically significant impact on cognitive performance and its trajectories, we will model data using interrupted time series analyses. Interrupted time series analysis is a powerful quasi-experimental design to study the longitudinal effects of interventions or exposures, accounting for pre-intervention/pre-exposure trends. We will adopt the approach described in Kontopantelis *et al.*, *BMJ* 2015.^{21 22} According to this approach we will use regression models in which the within patient performance variation over time is partitioned into three main components, to provide independent tests for the slope in scores in the pre-operative period (test 1); the change in level (i.e., absolute change) around surgery, allowing for the trend before surgery (test 2); and the change in slope from before to after surgery (test 3).^{21 22} The preoperative slope quantifies the trend in performance before surgery. The level change is an estimate of the absolute change in cognitive performance that can be attributed to surgery, i.e., between the time points immediately before and immediately after surgery, and accounting for the preoperative trend. The change in slope quantifies the difference between the preoperative and postoperative slope. Based on the hypothesis that the postoperative trajectory will not be homogenous over the 12 months after surgery, we will also adopt a more complex interrupted time series model that will allow for different slopes of change in different time segments, i.e. right before to 1 month after surgery, 1-3 months, 3-6 months, and 6-12 months after surgery.²³ We will conduct the primary analysis first considering only the early-intermediate postoperative performance (up to 6 months after surgery). With the assumption that the

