impact of surgery can last as long as one year,² we will repeat the analysis including also the change between 6 and 12 months after surgery. In our regression models, we will use estimates of error variance obtained from bootstrap techniques using 1000 bootstrap samples. We will analyze the performance at each task separately, and then combining the 4 scores into one unique measure of performance. We will explore whether clinically significant changes have occurred at any time point. There is no standard definition for what is a clinically significant perioperative decline across different tests.^{24 25} In addition to the change as defined in our sample size calculation (i.e. a change in score equal to or greater than the average difference in scores between a healthy older adult and a subject with MCI), we will consider also 2 most commonly adopted definitions, i.e. 1) a change of $\geq 20\%$ in test scores,²⁶ and 2) a reliable change index (RCI) of ≥ 1.65 . The RCI is an index commonly used in neuropsychology,²⁷ and also in studies using the CBB,¹³ calculated by dividing the individual's test-retest difference score by the standard error of that difference score, and can be interpreted as a standard Z score. The cut-off of RCI=1.65 is the point beyond which 5% of the values from the normal sample population will fall (i.e. $P<0.05$, one tailed test). We will compare the performance scores at each time point with the preceding time points, and evaluate the changes based upon these criteria. We will provide the number and percentage of patients experiencing a cognitive decline based on these definitions at each of the segments of the observation period. We will also compare our study population data with existing age-stratified normative data for the CBB.²⁸

In our primary analyses, we will include only patients who completed ≥ 2 assessments preoperatively and ≥ 3 assessments (i.e. 1, 3, and 6 months) postoperatively. Secondarily, we will repeat our analysis dealing with missing data 1) through multiple imputation techniques; and 2) using a method of evidence-informed data imputation, previously implemented in our studies, which takes onto account the reason for the missing data.³

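### The primary analysis admits only patients with all of the 1-, 3- and 6-month tests, so it selects on events after surgery and leaves out valid 6-month scores

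*Combined protocol and SAP*

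**What the plan says.** Section 3.6.1 (Primary analysis) sets the analysis set: "In our primary analyses, we will include only patients who completed" at least two assessments before surgery and at least three after it. The three are spelled out as months 1, 3 and 6, so each is mandatory. The next sentence begins "Secondarily, we will repeat our analysis dealing with missing data" and names two methods: multiple imputation, and an imputation that uses the reason a value is missing.

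Section 3.5 (Sample size) bases the primary hypothesis on OBK at one time point: "on average, in our population, the cognitive performance at 6 months after surgery will be worse" than the preoperative trajectory would predict. The size is justified as follows: "Based on a test of comparison of means in one sample", two-sided alpha 0.05, SD 0.16, 80% power, 330 enrolled, up to 10% attrition.

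The model in section 3.6.1 is an interrupted time series regression in which "within patient performance variation over time is partitioned into three main components". A fuller version allows "different slopes of change in different time segments". The plan will also report the "number and percentage of patients experiencing a cognitive decline based on these definitions at each of the segments" of follow-up.

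**The concern.** Only the postoperative half of the rule is at issue. The requirement of two preoperative tests follows from the design, which depends on a preoperative slope for each patient (section 1: "we will be able to draw preoperative individual-specific trajectories of cognitive performance").

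The postoperative half raises two problems.

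- **Selection after the exposure.** Whether a patient completes three home tests is settled after surgery, and surgery is the exposure under study. If patients who miss month 1 or month 3 decline more than the others, the primary estimate understates decline. If they decline less, it overstates it. The documents fix neither sign nor size.
- **Discarded data.** A patient with a 6-month OBK score, the quantity in the primary hypothesis, is left out for missing an earlier test. Nothing in the description of the regression is said to need complete postoperative records, and no reason for the rule is given. Precision is lost even if there is no bias, and the sample size has little room for it.

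**Working it through.** **Inputs from section 3.5.** Expected decrease over 6 months without a surgical effect: 0.009. Hypothesised decrease: 0.035. SD 0.16, two-sided alpha 0.05, power 80%, N = 330, attrition 10%.

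**The plan's own figure.** Difference = 0.035 − 0.009 = 0.026. Normal approximation: n = [(1.960 + 0.842) × 0.16 / 0.026]² = 297.2, and 297.2 / 0.9 = 330.3. The stated 330 reproduces. At 330 × 0.9 = 297, power is 80.0% (normal) or 79.7% (t). So 10% is the total loss from the analysis set that the plan can absorb at 80% power.

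**Assumptions.** The documents give no rate of missed tests. Let q be the completion probability per test, the same at each visit: 0.97, 0.95 or 0.90. Losses from the preoperative rule are left out of both sides of each comparison.

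**Counts with independent misses.**

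- Patients with a 6-month score: 330q
- Patients meeting the postoperative rule: 330q³
- Observed 6-month scores dropped: 330q(1 − q²), a share f = 1 − q² of those observed

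Power is from the one-sample two-sided t test with noncentrality 0.026√n / 0.16.

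| Missed per test | With 6-month score | Meeting rule | Dropped (f) | Power, all 6-month scores | Power, under rule |
|---|---|---|---|---|---|
| 3% | 320 | 301 | 19 (5.9%) | 82.6% | 80.2% |
| 5% | 314 | 283 | 31 (9.75%) | 81.9% | 77.8% |
| 10% | 297 | 241 | 56 (19.0%) | 79.7% | 71.0% |

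The standard error under the rule is larger by a factor 1/q, that is by 3%, 5% and 11%.

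**Counts with clustered misses.** Beta-binomial with intraclass correlation 0.3 (assumed), so a + b = 1/0.3 − 1 = 2.333 and a = 2.333q. The probability of completing all three is q × (a + 1)/3.333 × (a + 2)/4.333. For q = 0.90 this is 0.900 × 0.930 × 0.946 = 0.792, and 330 × 0.792 = 261.

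| Missed per test | Meeting rule | Dropped | Share f | Power under rule |
|---|---|---|---|---|
| 3% | 308 | 12 | 0.037 | 81.1% |
| 5% | 294 | 19 | 0.061 | 79.3% |
| 10% | 261 | 36 | 0.120 | 74.4% |

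**Dropout only.** If every patient who misses a test never returns, no one has a 6-month score without months 1 and 3, and the rule drops no 6-month scores. It still discards the month-1 and month-3 scores of patients who leave later.

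**Bias caused by the rule alone.** Hold the mean excess decline over all observed 6-month scores at 0.026, and let x be the mean among dropped patients. The retained mean is (0.026 − f·x)/(1 − f). Take x from 0 (no excess decline) to 0.052 (double); this range is assumed.

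| Missed per test | Independent: x = 0 to x = 0.052 | Change from 0.026 | Clustered: change, f/(1 − f) |
|---|---|---|---|
| 3% | 0.0276 to 0.0244 | ±6% | ±4% |
| 5% | 0.0288 to 0.0232 | ±11% | ±6% |
| 10% | 0.0321 to 0.0199 | ±23% | ±14% |

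At x = 0.026 the bias is zero.

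**The case against.** The strongest reply is that the plan already deals with this. Two imputation analyses are pre-specified, one of them informed by the reason for missingness, and both bring the dropped scores back. What remains is which analysis is called primary. The objectives speak of describing and exploring, and a fixed set of patients has a real use: the same people contribute to each slope segment and to each count of decliners. This stands as a reason to keep the complete-record analysis. It does not make that analysis the right one for the hypothesis in section 3.5, which is about the population average at 6 months. If the analyses disagree, the plan gives precedence to the selected subset.

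The second reply is that the size rests entirely on assumed rates and patterns. That is correct. Reminder calls and emailed links before each test should limit sporadic misses, though the documents do not say by how much. Clustering shrinks the effect, and pure dropout removes the loss of 6-month scores. At 3% missed, power is still about the promised 80%. Even the largest bias shown, 0.0061, is about 0.6 of a standard error (0.16/√241 = 0.0103). The power figures also describe the one-sample test, not the interrupted time series model. These points limit the weight of the concern without answering it.

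Third, a model using all available data assumes missingness at random and, unless the plan says otherwise, in effect extrapolates scores beyond death. Both are fair. The plan's multiple imputation shares both limits, and the documents do not say how either planned imputation treats deaths.

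**Conclusion.** The concern holds. As written, the analysis that carries the main conclusion selects patients on events after surgery and omits some observed values of its own endpoint. The consequence is moderate and uncertain. Under the assumed miss rates of 3% to 10%, between 12 and 56 valid 6-month scores are dropped, and power under the rule is 81% to 71%. With dropped patients' excess decline anywhere from none to double the average, the estimate shifts by up to 4% to 23% in either direction. It does not shift at all if they resemble the rest, and no 6-month scores are lost if missingness is pure dropout. The figure of 330 is not wrong; it holds if total loss from the analysis set stays within 10%. Bias from 6-month scores that are themselves missing is a separate matter, which this rule does not cause and no choice of analysis set fully removes. This is an inexpensive improvement, not a fatal flaw.

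**What to change.** Keep the requirement of at least two preoperative assessments and delete the requirement for all three postoperative ones. Then:

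- Make the primary analysis a likelihood-based mixed-effects interrupted time series model with patient random effects, using every available postoperative Cogstate assessment in the analysis window. Promoting the planned multiple imputation to primary would be a smaller edit that also restores the dropped scores.
- Move the complete-record analysis to sensitivity, where it still compares segments within the same patients.
- Keep both planned imputations and add a delta-adjusted check, for example shifting imputed OBK scores in steps from 0 to −0.07, the protocol's own healthy-to-MCI difference.
- Compare patients who meet the three-test rule with those who do not on data already collected: baseline characteristics, last Cogstate score, intercurrent events, LLFDI-FC, GDS and NPRS.
- State how deaths and inability to test are treated in the analysis.

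The cost is SAP wording and a little more analysis, with no new data. The new primary model relies on missingness at random and can still be biased if unobserved decline itself leads to missed tests, which is why the sensitivity checks are needed.

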3.6.2 Secondary Analyses

We will explore whether the effect of surgery on cognitive trajectories differ based on baseline patient characteristics, including age, type of surgery, cognitive performance at baseline, comorbidities, mobility, GDS and pain score. This will be done studying the interaction of these covariates with the components of the interrupted time analysis. The interrupted time series approach as described assumes linearity and constancy of the preoperative trend when projected postoperatively. We will evaluate the validity of these assumptions exploring the association of changes in cognitive performance with intercurrent events other than the index surgery, for the long-term effects.

With a similar approach as for the cognitive performance, we will study the perioperative trajectories of patient physical function/mobility (as indicated by the LLFDI-FC and the life space mobility questions), depressive symptoms (as indicated by the GDS), and of pain (as indicated by the NPRS). We will also explore whether the time-dependent LLFDI-FC, GDS and NPRS scores are associated with the time-dependent cognitive scores.

STATA software, version 15, will be used for the analyses.

4. IMPORTANCE OF THE STUDY

Capitalizing on one of the unfortunate consequences of the COVID-19 emergency, i.e. the deferral of many elective surgeries, our study will provide a unique insight into the role of surgery on perioperative and postoperative cognitive trajectories in older patients. At the same time, the study will enlighten on trajectories of patient reported outcomes, such as mobility, mood, and pain, in patients waiting for their delayed surgery in the COVID-19 era.

Our study will be also a proof of concept for a perioperative study design, which could be applied to a larger scale, and to other perioperative outcomes.

Finally, as an unintended positive consequence, this study will translate into a periodic tele-contact with older patients who, during and after the COVID-19 pandemic, will most suffer the consequences of the social distancing.

APPENDIX I. Study timeline, measurements, and data collection

Measurement	Before surgery				After surgery							
	- ≥6 weeks	Monthly		+1 mo		+3 mo		+6 mo		+12 mo		
	Videocoference with research team	Reminder call with research team*	Patient self-administered	Reminder call with research team*	Patient self-administered	Reminder call with research team*	Patient self-administered	Reminder call with research team*	Patient self-administered	Reminder call with research team*	Patient self-administered	
Verbal consent (confirmation)	x	x		x		x		x		x		
Sociodemographic and clinical data	x											
Intercurrent clinical events**		x		x		x		x		x		
Information on index surgery				x								
Cogstate Brief Battery (CBB)			x		x		x		x		x	
Change in activities and participation due to COVID-19	x											
Late-Life Function and Disability Instrument (LLFDI-FC) and life space mobility		x		x		x		x		x		
Geriatric Depression Scale (GDS)		x		x		x		x		x		
Numeric Pain Rating Scale (NPRS)		x		x		x		x		x		

*0-3 days before the expected self-administered cognitive assessment

**hospital admissions, ED visits, visits to urgent care, changes in medications

APPENDIX II. Performance at the Cogstate One-Back Task (OBK): interpretation and clinical relevance of changes in score

From Lim 2013¹³ and Mackin 2018¹⁹

Baseline score (SD) in HA	Average difference in score between HA and persons with MCI at any time point (Cohen's d)	Average difference in score between HA and persons with dementia at any time point (Cohen's d)	Score change per every additional year of age (population level)
1.35 (0.16)	0.07 (0.60)	0.17 (2.40)	-0.004

HA – healthy older adults

MCI - subjects with mild cognitive impairment

APPENDIX III. Changes in activities and participation since COVID-19 questionnaire

In the next set of questions, we will ask you about how your perceived functional ability and daily activities have changed since social distancing began due to COVID-19. You can reply by the following 5-point scale: much worse, a little bit worse, stayed about the same, a little bit better, much better.

Activities	Much Worse	A little bit worse	About the same	A little better	Much better
Your ability to move around in your home (such as walking, climbing stairs) become ...					
Your ability to engage in sports or recreational activity (such as casual/brisk walking, dancing, bowling, shuffleboard, hiking, Yoga, gymnastics, stationary bike,) become ...					
Your ability to engage in housework activity (such as dusting, washing dishes, and vacuuming) become ...					
Your ability to stay physically active (walking, exercise, working out) become..					
Participation	Much Worse	A little bit worse	About the same	A little better	Much better
Since social distancing began due to COVID-19 has ...					
Your ability to keep in touch with others (through letters, cell phone/phone or email) become ...					
Your ability to take care of your health (such as managing daily medications, following a diet, cooking your own meals, bathing, dressing and toileting) become ...					
Your ability to take care of your errands (such as buying groceries or taking care of finances) become ...					
Your ability to participate in the community and maintain a social life (e.g., volunteer, go to church, meet with others) become...					

REFERENCES

3. Neuro VI. Perioperative covert stroke in patients undergoing non-cardiac surgery (NeuroVISION): a prospective cohort study. *Lancet* 2019;394(10203):1022-29. doi: 10.1016/S0140-6736(19)31795-7
